The current IMDs guidelines are cautious about the recommendations on the use of CGM and its clinical practice application in nutritional improvements or modifications (15–17). Rossi et al. have recently proposed indications for CGM monitoring and CGM outcome parameters in patients with hepatic GSDs (14). Peeks et al. also indicated outcome parameters for hepatic GSDs (13).

Worth et al. have recently analyzed the state of art of the evidence for the use of CGM in non-diabetic children with hypoglycemia (9). Some suggestions for qualified CGM use have been provided, but a focus on patients' perspectives on the use of different CGM systems is still lacking, especially on recent tools developed by new technologies.

Study Objectives

Primary objective

Assessment of Pre-set targeted time in hypoglycemia and number of episodes of pre-set hypoglycemia during the different periods of use of CGM tools based on different alarms.

Secondary objectives

Accuracy of the two different CGM systems (comparator SBGM by capillary finger stick).

Assessment of patients' perspectives and tolerance to the use of two subsequent different CGM systems and tools, in particular on different types of alarms: Dexcom One Plus (Dexcom) with threshold alarm and Dexcom G7 (Dexcom) with predictive alarm.

Assessment of quality of life and sleep quality.

Assessment and comparison of glycemic control, patients' perspective and tolerance of CGM with USUAL Care CGM.

Study Design

Study Type

Prospective interventional with medical devices CE

Study Site

Sample Size Estimation

11 IMDs at risk for hypoglycemia

The rare condition of disorders investigated needs to be considered for the sample size (e.g. GSD I has a frequency of approximately 1 in 100,000 and the estimated incidence of CHI ranges between 1:27,000 and 1:50,000 live births in outbred western population).

Randomization

Patients will be randomized to start with the use of Dexcom G7 o Dexcom One Plus after baseline.

Methods for randomization: Randomization will be employed to assign participants to different

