Continuous Glucose Monitoring (CGM) systems to ensure unbiased comparisons across the study groups. Simple randomization using computer-generated random numbers will be implemented to allocate patients randomly. This method will help distribute confounding variables evenly between groups, thereby minimizing selection bias. Block randomization may also be utilized to maintain balance in the number of participants among the groups throughout the study. Allocation concealment will be maintained until the intervention assignment to prevent any potential influence on patient enrollment.

Statistical method

Definition of Analysis Sets

The following data sets will be analyzed:

- Full analysis set (FAS):
The set of subjects is as close as possible to the ideal implied by the intention-to-treat principle. All subjects with at least one efficacy follow-up will be included. It is derived from the set of all eligible subjects by minimal and justified elimination of subjects. When handling of missing values of primary outcomes, the last observation carried forward (LOCF) method will be applied.
- Per-protocol analysis set (PPS):
The per protocol analysis set will consist of all patients in the full analysis set plus the following criteria: completion the treatment process, without any major protocol violations, good compliance (80%~120% medical device and capillary finger sticks compliance) and without missing value in primary outcomes. Patients with at least one major protocol violation (e.g missing the 8 weeks efficacy follow up) will be excluded from the per-protocol analysis.
- Safety Set (SS):
The safety set will consist of all subjects followed at least one period with one CGM system.

Endpoints:

Primary: number of episodes of pre-set hypoglycemia (hypoglycemia <70 mg/dL and severe hypoglycemia < 54 mg/dL), time above, under or in pre-set target range, glycemic variations during the different periods of use of CGM tools based on different alarms;

Secondary objectives

Secondary: accuracy and MARD (comparator finger capillary sticks) during the use of two different CGM; perspectives and preferences in monitoring and specific use of different alarms with Dexcom One Plus or with Dexcom G7; correlation of primary endpoint with the quality of sleep, quality of life and/or neurocognitive outcomes i.e. attention, assessed by specific questionnaires; perspectives and preferences in monitoring and specific use of different CGM with Usual Care monitoring.

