Statistical Analysis (example)

(1) General Principles

Quantitative variable will be described by the total number of cases, number of missing values, mean, and standard deviation, minimum, maximum and median. Categorical variables will be described by the number of cases and percentages.

All statistical tests will be performed using two-sided test, P value less than or equal to 0.05 will be considered to have examined the difference statistically significant (Unless otherwise noted). For comparison between two groups of the general condition, the suitable method shall be adopted to conduct analysis according to the type of indicators; for the comparison among groups of quantitative data, group t test (homogeneity of variance, normal distribution) or Wilcoxon rank-sum test will be adopted according to the data distribution (the Shapiro-Wilk test will be used beforehand to check whether the variables follow a normal distribution or not); for categorical data, the chi-square test or Fisher's exact test (if the chi-square test is not applicable) shall be adopted; for ordered data, Wilcoxon rank-sum test or Cochran-Mantel-Hansel test shall be adopted. Multiple regression analyses will also be considered, including linear regression for continuous dependent variables, Poisson regression and cumulative logit logistic regression for ordered response variables (or logistic regression for dichotomous variables, such as presence/absence). Moreover, ANOVA or mixed-effects models will be used to compare how the effect of interest varies over time within the same subject, repeated measures.

(2) Completion and Baseline Parameters

The summary of the study completion includes the count of completed cases of each study center, the list of dropout cases, the analysis set description, the comparison of dropout rates of the groups and the list of reasons for incompleteness. The summary of baseline parameters includes demographic characteristics (gender, age, height, vital signs etc.), history of illness and medications, and specific Questionnaires about CGM tolerance, perspectives and expectations. Comparisons among the two different CGM devices groups and gold standard by capillary finger stick will be conducted to evaluate MARD and reliability during the period of observation.

(3) Compliance

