- Compliance of study: study compliance to the CGM two medical devices and capillary finger sticks of all groups will be described and compared. A list of subjects with poor compliance (80% below or 120% above compliance) will be generated.

Observation parameters list (CRF)

Patients at screening, baseline, after 30 days of **unblinded monitoring** with Dexcom G7 and 30 days of **unblinded monitoring** with Dexcom One Plus (Fig. 2). The start of the single CGM tool will be randomized (i.e. 50% of patients will random start with G7 and then switch to Dexcom One Plus, and *viceversa*).

- 1) SCREENING _ General data collection: age, gender, height, body weight, minority, career, income, degree of education, family history, smoking habit, primary diseases or accompanied diseases.
- 2) SCREENING _ Previous glucose monitoring (referring to the last 8 weeks): number of capillary fingers sticks per day, use (or not) of CGM and type of CGM device
- 3) SCREENING _ Major comorbidities
- 4) SCREENING _ Document intake of medications
- 5) SCREENING _ Adverse events and the rate of hospitalization during the last year
- 6) BASELINE _ Quality of Life (SF-12 rating scale)
- 7) BASELINE _ Quality of Sleep (Pittsburgh sleep quality index (PSQI))
- 8) FOLLOW UP _ Capillary finger sticks glucose values (3 per day) by diary record

- 9) FOLLOW UP_ CGM values: time above, under or in the pre-set target, number of episodes of pre-set hypoglycemia
- 10) FOLLOW UP_ CGM tolerance, perspectives and expectations (Specific questionnaires)
- 11) FOLLOW UP_ CGM Quality of Sleep (Pittsburgh sleep quality index (PSQI), quality of life (SF12))
- 12) FOLLOW-UP_ Education on the use of CGM device (sensor, receiver or other tools)

Flowchart indicating which parameter is measured when:

Observation Parameters	Screening	Enrollment/Baseline	Follow up - After 30 days	Final Visit study - After 30 days
Informed consent	x			
Demographic (Age, Gender, Career, Degree of Education, Income)	x			
Height	x			
Body Weight	x	x	x	x
Family History	x			
Smoking Habit	x			
Physical exam	x			
Vital signs	x			
Primary Diseases or Accompanied Diseases	x			
Major IMD Comorbidities	x			
Glucometer values		x	x	x
Use of CGM	x			
Documented Intake of Medications	x			
Rate of Hospitalization During the Last Year	x			
Type of CGM Device	x	x	x	x
Capillary finger sticks glucose values (3 per day)		x	x	x
CGM values (time in pre-set hypoglycemia, number of pre-set hypoglycemia, MARD)		x	x	x

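### The finger-stick reference for MARD is collected by diary during unblinded sensor use, and the separately scheduled glucometer values are given no role in it

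*Combined protocol and SAP*

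**What the plan says.** Accuracy is the first secondary objective, with capillary finger sticks as comparator. The Endpoints section lists "accuracy and MARD (comparator finger capillary sticks) during the use of two different CGM". Statistical Analysis, (2) Completion and Baseline Parameters, says that comparison with the "gold standard by capillary finger stick will be conducted to evaluate MARD and reliability during the period of observation".

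The Observation parameters list (CRF), item 8, gives the collection method: "FOLLOW UP _ Capillary finger sticks glucose values (3 per day) by diary record". The same section describes each 30-day device period as "unblinded monitoring".

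The flowchart has one row for finger-stick values and a separate row, "Glucometer values". Both are marked at baseline, the 30-day follow-up and the final visit, as is the CGM row that contains MARD. The meter row is not defined and is not tied to MARD.

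The plan sets no clock times for the three daily sticks, no rule for pairing a stick with a sensor reading, no alignment of clocks and no check of diary against meter. Its stated controls are 80% to 120% compliance (Definition of Analysis Sets; Statistical Analysis, (3) Compliance) and random examination of CRFs (Study Quality Control).

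The secondary objectives contrast "Dexcom One Plus (Dexcom) with threshold alarm and Dexcom G7 (Dexcom) with predictive alarm".

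**The concern.** MARD is the mean of |sensor − reference| / reference over matched pairs. It is only as good as the value and the time of the reference, and a diary kept by someone who can see the sensor is weak on both.

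- **Time.** If the recorded time is off, the stick is paired with a sensor reading from a different moment. While glucose is moving, that gap counts as sensor error and MARD rises.
- **Selection.** A patient who sees a large disagreement may repeat the stick, or not write it down. Losing discordant pairs lowers MARD.

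At stake is whether the reported accuracy of either system in this population can be read at face value. A time that was never captured cannot be recovered later, and a diary alone does not show what was left out. If the meter stores time-stamped results, it addresses both problems, and a visit slot for meter values already exists.

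**Working it through.** The documents give no expected MARD, accuracy limit or pairing window, so there is no planned figure to reproduce. The calculations below show size and direction under stated assumptions.

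**From the documents.** 11 patients, 3 sticks per day, 30 days per device.
- Planned pairs per device: 11 × 3 × 30 = 990.
- Per patient and period: 3 × 30 = 90. The 80% rule then needs 0.80 × 90 = 72, if compliance means the share of planned sticks recorded.

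**Assumed.** True MARD 8.5%; glucose mean 95 mg/dL, SD 20; proportional, normally distributed sensor error e. For a normal error, mean |e| = SD × √(2/π), so SD = 8.5% / 0.798 = 10.65%.

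**1. Time-entry error (simulation)**

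Sensor value = G × (1 + e) + r × t, where G is glucose, r the rate of change (normal, mean 0) and t the time error (uniform between −J and +J minutes). Observed MARD:

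| Slope SD (mg/dL/min) | J = 0 | J = 10 min | J = 15 min |
|---|---|---|---|
| 0.5 | 8.5% | 8.9% | 9.3% |
| 1.0 | 8.5% | 9.9% | 11.3% |
| 1.5 | 8.5% | 11.3% | 13.7–13.8% |

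**2. Selective recording (closed form)**

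Suppose half of the pairs with |e| above 15% are not recorded.
- Cut-off: 15 / 10.65 = 1.41 SD. Share of pairs beyond it: 15.9%.
- Pairs kept: 1 − 0.159/2 = 92.0%, or about 83 of 90 per patient and period, above the 72 required.
- Contribution of the pairs beyond the cut-off to the mean: 3.15 points.
- Observed MARD: (8.5 − 3.15/2) / 0.920 = 7.5%.

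**3. Different assumptions**

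True MARD 10%, reference 90 mg/dL, normally distributed time error, slope SD 0.5 to 2 mg/dL/min:
- Time-error SD of 5 minutes: 10.2% to 13.0%.
- SD of 10 minutes: 10.9% to 18.5%.
- SD of 15 minutes: 11.8% to 24.7%.
- Half of the pairs beyond 20% omitted: 9.1%, with 94.5% kept.
- Half of the pairs beyond 15% omitted: 8.5%, with 88.4% kept.

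The directions are the same. The size depends heavily on the assumed slope and time error.

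**4. Difference between devices**

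Time error of equal size on both devices inflates both MARDs. Each patient uses both devices, so stable habits of rounding or omission largely cancel in the comparison. A false difference needs timing or omission that changes with the device. The alarms give a possible route: stick times are free, and a predictive alarm may prompt a stick at a different glucose level or slope than a threshold alarm. The documents provide nothing from which to size this.

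**The case against.** The best defence is that the meter may already be the intended source. The glucometer row falls at the same visits as the MARD row and could be the memory read proposed here. This stands in part: the plan never names the source of the MARD reference. But item 8 is the only place that states how finger-stick values are collected, and it says diary, so the text needs changing on either reading.

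The defence is also right that MARD is secondary. CRF item 9 takes the hypoglycemia and time-in-range measures from CGM values, so the data source of the primary endpoint is untouched.

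Three stronger readings are tempting and are not supported:

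- **That the diary is hand-written, or that its times are known to be wrong.** The text does not say whether the diary is paper or electronic, or whether a clock time is entered. The errors are an exposure, not an established fact.
- **That MARD is biased in a known direction.** Time error raises it and omission lowers it, so the net sign is unknown.
- **That the alarm types produce a false device difference of a given size.** With a constant error of 8 mg/dL, sticks at 65 rather than 80 mg/dL give 12.3% against 10.0%. If one third of sticks are alarm-driven, the gap is 2.3/3 = 0.8 points. With sticks at 65 and 70 mg/dL and 10% alarm-driven, it is 0.1 × (12.3 − 11.4) = 0.09 points. Under the proportional error used above, MARD does not depend on glucose level and the gap from level alone is zero. The answer is set by inputs that the documents do not contain.

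**Conclusion.** The point holds as a weakness in a secondary endpoint that should be put right before data collection. The only stated recording method for the MARD reference is a diary kept during unblinded use, and the scheduled meter values have no stated role in MARD.

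With an assumed true MARD of 8.5%, plausible time error alone moves the observed figure to between 8.9% and 13.8%. Omitting half of the pairs beyond 15% moves it to about 7.5% without breaching the compliance rule. These figures illustrate scale; they do not predict this trial's result. They rest on the assumed error model, slopes, time errors and omission rate. A spurious device difference remains possible but unquantified, and the crossover protects against the part due to stable patient habits.

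**What to change.** Change CRF item 8 and the accuracy analysis as follows:

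1. Make the time-stamped readings in glucometer memory the MARD reference, read at the visits where meter values are already scheduled. State in the flowchart that this is the purpose of that row.
2. Use the same meter in both periods, and align its clock with the CGM receiver or phone at each visit.
3. Pair each meter reading with the nearest sensor value within a pre-stated window, for example 5 minutes.
4. Keep the diary as back-up and for context, such as marking sticks prompted by an alarm.
5. Keep all meter-recorded pairs in the main MARD. Report MARD by glucose range, and with and without alarm-prompted sticks as a sensitivity analysis.

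Restricting the main comparison to sticks at fixed times would equalise timing between devices, but it could thin the pairs below 70 mg/dL, the region that matters most for this trial. Step 5 avoids that loss.

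The cost is revised CRF and patient-instruction wording, plus a memory read and clock check at existing visits. Readings will be lost where the meter memory is incomplete; diary values used in their place should be flagged.

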Quality of Life Evaluation: SF-12 Rating Scale		x	x	x
Specific Questionnaires for CGM Tolerance, Perspectives, and Expectations		x	x	x
Quality of Sleep: Pittsburgh Sleep Quality Index (PSQI)		x	x	x
Education on the use of CGM device		x	x	x

Study Population

Inclusion Criteria

Adult patients with Glycogen Storage Disease (GSD) or Congenital Hyperinsulinism (CH), aged over 18 years, who have had at least one clinical and biochemical follow-up at the hospital outpatient service within the last year or two years. This includes patients with a biochemical or genetic diagnosis of GSD or CH.

Exclusion Criteria

Inability to sign consent or comply with study procedures. No additional conditions are expected that could introduce bias in the results and therefore require further exclusion criteria.

Study Evaluation

The Ethics Committee of every study site will guarantee the safety of the subjects, receive the effective data and conduct the review on process analysis, and ensure that this study is conducted as per the highest standard of ethics.

Study Quality Control

This study will be conducted by trained and qualified investigators. The investigators shall fill in the CRF in a trustful, detailed and earnest manner to ensure that the content included in the CRF is complete, authentic and reliable. During the study process, the study institution shall conduct examination against case report forms randomly.

Requirements of Ethics

This study complies with the Declaration of Helsinki (version 2000) strictly, and will be conducted as per the relevant medical research regulations and provisions in Italian country.

Before the subjects are included in this study, the investigators are responsible for introducing the purposes, procedures and potential risks of this study to the subjects and their guardians in a complete and comprehensive manner in writing. The subjects have the right to withdraw from this study at any time. Prior to the commencement, it is essential to receive the written informed consent of each subject, which shall be reserved for filing as a clinical research document.

Management Principles

Resume

The latest resume of each investigator and collaborator shall be submitted to the study institution prior to the commencement of this study.

Record Storage in the Study Site

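### Each study device is rated for tolerance only at its own 30-day visit, so a patient who leaves early because of a device and misses that visit never rates it

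*Combined protocol and SAP*

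**What the plan says.** Under Secondary objectives, the protocol sets out to assess patients' "perspectives and tolerance to the use of two subsequent different CGM systems and tools", contrasting a threshold alarm with a predictive one.

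The Observation parameters list (CRF) gives the assessment times as "Patients at screening, baseline, after 30 days of" use of one device and 30 days of the other, in randomised order. The flowchart that follows has four columns: screening, baseline, the first 30-day visit and the final visit 30 days later. The row "Specific Questionnaires for CGM Tolerance, Perspectives, and Expectations" is marked at the last three, as are the SF-12 and PSQI. The Randomization section starts the study devices after baseline. There is no column for early withdrawal, although Requirements of Ethics lets patients leave whenever they wish.

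On missing data, the full analysis set paragraph says: "When handling of missing values of primary outcomes, the last observation carried forward (LOCF) method will be applied". No rule is given for the questionnaires. Completion and Baseline Parameters plans a dropout list, a comparison of dropout rates and the reasons. Compliance plans a comparison of adherence to the two devices and a list of poorly compliant patients.

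The safety set is defined thus: "The safety set will consist of all subjects followed at least one period with one CGM system".

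**The concern.** Abandoning a device is about the clearest sign that a patient does not tolerate it. Under this schedule, someone who leaves the study for that reason before the 30-day visit supplies no tolerance, sleep or quality-of-life rating for that device. The ratings that go missing are then probably the poor ones, and the device stopped more often looks better than it is. A rating not collected at the time cannot be recovered by a later choice of analysis, so the remedy has to be in the CRF.

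There is a smaller, separate matter. On its natural reading, the safety set leaves out a patient who wore a study device and left during period 1. A safety set would normally include everyone exposed.

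**Working it through.** **Does anything in the plan supply the missing rating?**

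- The baseline form precedes both study devices, so it cannot rate either of them as used in the study.
- LOCF is stated for primary outcomes only. Applied to tolerance, it would carry forward a baseline form or a rating of the other device.
- Dropout reasons and compliance figures show that a device was stopped and perhaps why. They are not a questionnaire score.
- A mixed-effects model, one of the options under General Principles, cannot use a score that was never collected.

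**How large could the effect be?** The plan has no figure to reproduce. The 11 patients are justified by disease rarity, with no dropout allowance, rating scale or within-patient correlation. What follows is illustration on stated assumptions.

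Inputs: N = 11 (Sample Size Estimation). Completers rate both devices equally (set to 0). Each of k leavers, all on device A, would have rated it −D. The correlation between a patient's two ratings is r, assumed known, with equal variances and no period term. The hidden difference is the estimate of A minus B without the leavers' forms, minus the estimate with them.

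*Period-1 leavers (no rating of B).* Without the forms the estimate is 0. With them, the mean for A is −Dk/11. The random-intercept model shifts the mean for B by r times the shift in A, to −rDk/11. Hidden difference = D(1 − r)k/11. An unpaired comparison corresponds to r = 0.

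| k | r = 0 | r = 0.3 | r = 0.5 | r = 0.7 |
|---|---|---|---|---|
| 1 | 0.091D | 0.064D | 0.045D | 0.027D |
| 2 | 0.182D | 0.127D | 0.091D | 0.055D |
| 3 | 0.273D | 0.191D | 0.136D | 0.082D |

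*Period-2 leavers who rated B as completers did.* Without the forms the estimate is 0. With them it is −Dk/11. Hidden difference = Dk/11 at every r, and the same in a strictly paired analysis: 0.091D, 0.182D and 0.273D for k = 1, 2, 3. If they also rated B lower by E, the random-intercept figure is (D − rE)k/11. For k = 1, E = 0.5D and r = 0.5 this is (1 − 0.25)D/11 = 0.068D.

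*Sensitivity.* With a period term and a 6/5 or 5/6 split of sequences, one period-1 leaver at r = 0.5 hides 0.044D to 0.055D, and one period-2 leaver 0.083D to 0.100D. With one period-1 leaver on each device, the hidden difference is zero.

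**Against sampling error.** Assume a rating SD of 1 and r = 0.5. From ten complete pairs, the standard error of the device difference is √(2(1 − 0.5)/10) = 0.32 SD. One leaver hides 0.045 to 0.09 SD if D = 1 SD, and 0.09 to 0.18 SD if D = 2 SD, both below one standard error. Three leavers from one device with D = 2 SD hide 2 × 0.136 = 0.27 to 2 × 0.273 = 0.55 SD, against √(1/8) = 0.35 SD from eight pairs.

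**How likely is any leaver?** The plan gives no rate. At assumed per-patient rates of 5%, 10% and 20%, the chance of at least one among 11 is 1 − 0.95^11 = 43%, 1 − 0.90^11 = 69% and 1 − 0.80^11 = 91%. These count leavers for any reason, not only because of a device.

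**The case against.** The other side has a good deal to say, and much of it stands.

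- A reader might infer that anyone who gives up a device goes unrated. That is too strong: a patient who removes the sensor but attends the 30-day visit is rated. The study is single-centre, in patients under regular outpatient follow-up, so late contact is feasible. The text does not require it, however, and the gap remains for those who leave the study and miss the visit.
- The dropout and compliance reporting would probably show early stops by device. This makes a separate table of them a matter of presentation. It does not supply the rating.
- The contents page lists a schematic plan and a Figure 2 that are not in the available text. A withdrawal assessment could be mentioned there. The figure's caption speaks only of sensor changes and device switches, and the flowchart that is available has no such visit.
- A reader might infer that the tolerance comparison is seriously biased. The documents give no stopping rate or scale to support that, and one leaver's effect is below one standard error on the assumptions above. A strictly paired analysis could not use a period-1 leaver's form even if it were collected.
- A reader might infer that the safety-set wording distorts safety results. No safety endpoint or analysis is described, and adverse events appear only as history at screening. The wording could also be read loosely, as having entered a period.
- A reader might infer that the full analysis set also drops early leavers, because "All subjects with at least one efficacy follow-up will be included" leaves the follow-up undefined. The same paragraph opens with "The set of subjects is as close as possible to the ideal implied by the intention-to-treat principle", which favours keeping anyone with sensor data. That is not a defect to press.

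**Conclusion.** The point holds as a minor one. In the available schedule, each device has a single rating of tolerance, sleep and quality of life, and a patient who leaves the study early because of that device and misses the visit never gives it. The direction is predictable if leavers are dissatisfied: the comparison tends to favour the device stopped more often. The size is unknown. It is Dk/11 for period-2 leavers who rated the first device as completers did, and D(1 − r)k/11 for period-1 leavers in a random-intercept model. It is probably small with one leaver, and could exceed a standard error only if several patients left the same device with very poor ratings. The conclusion assumes that the missing schematic plan and figure add no withdrawal assessment. The safety-set wording deserves correction, but no described result depends on it.

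**What to change.** When a device is stopped early, have the patient complete the existing tolerance questionnaire, PSQI and SF-12 at that time, by phone if needed. Record the device, date and reason, and flag the shorter exposure in the data.

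As a minor correction, define the safety set as all patients who wore a study device.

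Showing early stops by device beside the tolerance results is optional.

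The cost is a CRF trigger for forms already in use and one reworded sentence; no new instrument or extra patients are needed. The downsides are that some leavers will decline and that early forms reflect less than 30 days of use, so the gap is reduced and not closed. The period-1 benefit also depends on using an analysis that can include a patient with one rating.
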